6.2. Primary Safety Endpoint

The primary safety endpoint is:

Composite Major Adverse Event (MAE) Rate at six (6) months post-treatment including:

- All-causes of death

 neuroloop	Confidential	Protocol – The baroloop Study
--	---------------------	-------------------------------------

- Hospitalization for hypertensive crisis
- Any device or procedure-related serious adverse event

All MAEs to be adjudicated by an independent Data Management Safety Board (DSMB).:

6.3. Primary Feasibility Endpoint

The primary feasibility endpoint is technical success, defined as the ability of the baroloop System to be placed around a vagal nerve and the ability to stimulate at 14 days post-implantation.

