2.5.2. Vagal Nerve Stimulation (VNS) – state of the art

Over 100.000 patients have been treated with vagal nerve stimulation (VNS) therapy for epilepsy. The surgical procedure to implant the vagal nerve stimulator is well established and appears to be a relatively safe intervention (Garcia-Navarrete et al., 2013; Kahlow and Olivecrona, 2013; Revesz et al., 2016). VNS surgery is associated with an overall surgical complication rate of 8.5% (Selner et al., 2019). “Surgical complications included infection, vocal cord palsy, post-operative hematoma, intra-operative bradycardia during test stimulation, and others, with infection (3.9%)” (Selner et al., 2019). A 6.5% rate of hardware complications were reported, including lead fracture and stimulator malfunction. Lead fracture was the most common complication (5.6%) (Selner et al., 2019). Overall, the implantation is a safe procedure and well established for more than 25 years (Spuck et al., 2010), and VNS is as a relatively safe treatment (Giordano et al., 2017; Panebianco et al., 2016; Selner et al., 2019).

Specifically with respect to vagal nerve stimulation to control blood pressure, selective stimulation of vagal afferent baroreceptor fibers is preferable to stimulating efferent fibers that may lead to side effects such as bradycardia or heart block (Plachta et al., 2014; Timarova and Steno, 2017). Most of the stimulation associated side effects are derived from stimulation of the inherent functions of the vagal nerve (Timarova and Steno, 2017). The feasibility of selective VNS to elicit baroreflex responses has been shown in rats without occurrence of severe adverse events (bradycardia or heart block) (Plachta et al., 2014). Even when angiotensin converting-enzyme inhibitors (a commonly used antihypertensive medicine) were co-administered with VNS, selective VNS reduced blood pressure (Gierthmuehlen et al., 2016). Moreover, cardiac-cycle-synchronized stimulation triggered to the R-wave of the electrocardiogram in rats successfully reduced blood pressure using constant stimulation parameters with hardly any side-effects (Plachta et al., 2016).

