4.4. Number of Subjects and Sites

Up to 10 subjects may be enrolled at up to 3 clinical study centers.

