4.11. Enrollment

Patient eligibility will be confirmed prior to insertion of the investigational device, and subjects will be considered enrolled in the study at the time that the skin is broken to implant the baroloop System.

Subjects who sign consent but are excluded before enrollment will not be included in the primary analysis of the study endpoints. The reason for exclusion will be documented in the Consent and Screening Log and the consent document maintained in the site's study records.

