1. If the patient is not judged to be ready for a first titration on day 14, the patient may return on or before day 21 for the first titration.
2. The first titration of blood pressure using baroloop stimulation (not earlier than 14 days after surgery when wound healing is complete) will be followed by a brief, one day hospitalization to observe the initial response to baroloop therapy.

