If a 20% reduction in baseline blood pressure is greater than the age-adjusted OBP target, then the target blood pressure should be approached in a series of incremental steps in which an intermediate target blood pressure not below 80% of the baseline blood pressure is targeted. This intermediate target blood pressure should then be maintained for a week (at least) until the next visit for further titration, when a further 20% reduction in blood pressure may be targeted so long as the patient has no symptoms of dizziness, orthostatic hypotension or other adverse effects

Once an effective set of stimulation parameters has been selected, this setting should be used for treatment until the next study visit, when the blood pressure response can be re-evaluated, and stimulation parameters may be adjusted as appropriate to reach the goal of a blood pressure less than the age-adjusted OBP target.

Once the first treatment stimulation level has been selected, the patient should be observed in the hospital for 24 hours (as noted above). The titration of blood pressure will be retested after 24 hours prior to discharge following the titration strategy described above over a more limited range of electrode combinations and preset stimulation values. If the treatment is well tolerated and no adverse effects of VNS are identified during the hospital stay, the patient may be discharged on the prescribed pattern of VNS. Patients need not be hospitalized following subsequent blood pressure/stimulation titrations so long as the patient has no symptoms of dizziness, orthostatic hypotension or other adverse effects.

It is the Sponsor's expectation that most patients will achieve an OBP less than the age-adjusted target of hypertension treatment within a small number of weekly titration sessions. If the titration process persists beyond 12 sessions (~ 3 months), it is permissible to extend the interval between titrations up to six weeks. The patient and physician may work together to achieve a titration schedule that achieves the age-adjusted target OBP as quickly as is safe.

N.B.: The IPG should be charged at every visit to the physician's office for follow-up. In the first four weeks of titration, the IPG will be recharged twice a week. After four weeks of titration, the IPG may be charged weekly when the well-being of the patient will also be assessed. There is no home charging possible in this First in Human Study.

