6.6. Imputation of Missing Data

Imputations for missing data in (e.g. withdrawn subjects, loss to follow-up, missing data) will not be performed. Analyses will be performed with all available data only.

7. Adverse Event and Incident Reporting

The occurrence of Adverse Events will be monitored during this study. All Adverse Events will be recorded on the Adverse Event Form and followed until resolved. The study will be conducted in accordance with EN ISO 14155: 2018-08: Clinical investigation of medical devices for human subjects - Good Clinical Practice. All Serious Adverse Event will be adjudicated by an independent DSMB and adjudicated results will be included in the data analysis.

 neuroloop	Confidential	Protocol – The baroloop Study
--	---------------------	-------------------------------------

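### An implanted subject not yet stimulated by Day 21 has no stated score on the primary feasibility endpoint, and one reading of the missing-data rule drops that subject from the rate

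*Combined protocol and SAP*

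**What the plan says.** Section 6.3 names technical success as the primary feasibility endpoint, "defined as the ability of the baroloop System to be placed around a vagal nerve and the ability to stimulate at 14 days post-implantation". The synopsis and 4.2.2 place the assessment at Day 14/21. The Procedural Success entry in section 12 returns to 14 days and adds that stimulation must be effective, without defining that word. Section 4.1 goes further and counts the ability to lower blood pressure as part of feasibility.

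The timing of the first test is in the notes to 4.23. Titration begins "not earlier than 14 days after surgery when wound healing is complete". If the subject is not ready on Day 14, "the patient may return on or before day 21 for the first titration". Nothing is said about a subject who is still not ready then. Section 4.22 requires the generator to be inactive during recovery, and states that the intra-operative test is not a guide to therapy.

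On who is counted:
- Section 4.11: "subjects will be considered enrolled in the study at the time that the skin is broken".
- Section 6.1: the primary endpoints are analysed by intention to treat with data from every enrolled subject. The next sentence confines the primary analysis to technical successes.
- Section 6.6: no imputation, and "Analyses will be performed with all available data only".
- Section 4.4: "Up to 10 subjects may be enrolled at up to 3 clinical study centers".

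**The concern.** The endpoint needs a stimulation result inside a short window, and the protocol foresees reasons why the result may not exist by then. Sections 2.5.2 and 5.3 list infection and hematoma among the expected surgical complications. A subject whose wound has not healed by Day 21 has been enrolled and implanted but has had no post-operative stimulation test. That subject has neither an observed success nor an observed failure.

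Two analysts following the plan could treat this subject differently. One keeps the subject in the denominator under 6.1; the other removes the subject under 6.6. Removal is not neutral, because it takes out subjects in whom the early course went badly and can only leave the rate the same or raise it. The success criterion in 6.1 and the stopping rule in 9.13 count only failures to implant, so neither registers a device that was implanted but not stimulated in time. If scoring is left open, the choice may be made after the results are known.

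**Working it through.** The plan states no target rate, power or sample-size calculation, so there is no figure of its own to reproduce. The check compares denominators.

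**Inputs.** N = 10 enrolled, the maximum in 4.4. Let f be the subjects observed to fail, u the implanted subjects untested by the end of the window, and s = N − f − u the successes. The values of f and u are assumptions.

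**Formulas.** All enrolled, untested scored as non-success: s/N. Available data only: s/(N − u). The difference is s·u / [N(N − u)]. Since s cannot exceed N − u, the difference is at most u/N, that is, 10 points per untested subject at N = 10. It is larger with fewer enrolled: 1/8 = 12.5 points at N = 8. Intervals are exact (Clopper-Pearson) 95%.

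| f | u | All enrolled | Available data only | Difference |
|---|---|---|---|---|
| 0 | 1 | 9/10 = 90% (55.5–99.7) | 9/9 = 100% (66.4–100) | 10 points |
| 0 | 2 | 8/10 = 80% (44.4–97.5) | 8/8 = 100% (63.1–100) | 20 points |
| 1 | 2 | 7/10 = 70% (34.8–93.3) | 7/8 = 87.5% (47.3–99.7) | 17.5 points |
| 2 | 1 | 7/10 = 70% (34.8–93.3) | 7/9 = 77.8% (40.0–97.2) | 7.8 points |
| 4 | 2 | 4/10 = 40% (12.2–73.8) | 4/8 = 50% (15.7–84.3) | 10 points |

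The intervals are wide and overlap. They are shown for scale only; 6.5 plans number and percent for categorical variables.

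**How many subjects might be untested.** The documents give no rate of delay past Day 21. Section 2.5.2 gives figures for comparable surgery: "VNS surgery is associated with an overall surgical complication rate of 8.5" percent, of which infection is 3.9%, and 6.5% hardware complications, of which lead fracture is 5.6%.
- Infection only: 10 × 0.039 = 0.39 subjects expected; chance of at least one = 1 − 0.961^10 = 33%.
- Any surgical or hardware complication, assuming independence: 1 − (0.915)(0.935) = 14.4%, or 1.4 of 10; chance of at least one = 1 − 0.8555^10 = 79%. With no overlap between the two kinds it would be 8.5 + 6.5 = 15.0%.

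The second figure is a loose upper bound. The surgical rate includes events with no stated link to wound healing, such as vocal cord palsy and intra-operative bradycardia. Hardware faults would mostly show up as failures when the device is tested. No timing is given for either kind.

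**The case against.** The strongest reply is that 6.1 already settles the matter. Primary endpoints are by intention to treat, enrolment is at skin incision, and 4.35 requires every enrolled subject to be accounted for. A reader might infer from 6.6 that the plan definitely removes untested subjects; the documents do not say so, and this is one of two readings. What stands against the reply is that 6.1 names the set of subjects but gives no score to a member of that set who has no test.

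Other stronger readings are also unsupported.

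- *All early failures are missing data.* A subject in whom stimulation is attempted and does not work is an observed failure. One explanted before first titration has no device able to stimulate, and is plausibly an observed failure on the wording of 6.3. Section 6.6 does not reach observed data.
- *Subjects with adverse effects at every setting have no score.* On the literal wording of 6.3 they are successes, because the device can stimulate. The difficulty is ambiguity: section 12 asks for effective stimulation and 4.1 for a fall in blood pressure.
- *Such subjects should fail if not discharged on stimulation.* Section 4.24 says "If the treatment is well tolerated and no adverse effects of VNS are identified during the hospital stay, the patient may be discharged", which concerns the first stay only. The same section provides for weekly titration afterwards, so a lack of therapy does not follow from the first session. A discharge-based criterion would turn a technical endpoint into a different one.

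It is also fair to say that no decision hangs on this rate. The study is descriptive, and its success and stopping rules count failures to implant. That limits the weight of the point but leaves a primary result open to two values. The sentence in 6.1 confining the primary analysis to technical successes is a separate problem: applied to this endpoint, it would make the rate 100% by construction.

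**Conclusion.** The point holds in a limited form. No section scores an implanted subject whose first stimulation test has not taken place by Day 21, and 6.1 and 6.6 point in different directions. The time point itself differs between sections, so a first test between the end of the 14-day visit window and Day 21 is also unclear under 6.3.

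On the available-data reading, the reported rate rises by up to 10 points for each such subject at N = 10. The size rests on assumed counts. If infection were the only cause and every infection delayed testing, about 0.4 of 10 subjects would be affected. A reader might take 14.4% as the expected share, but the documents support it only as a loose upper bound. Two untested subjects of 10 is therefore an illustration, above even the 1.4 that this bound implies. The effect is on a descriptive primary rate and not on a test or a stopping decision. The change is worth making because it is cheap and removes a choice that could otherwise be made after the data are seen.

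**What to change.** Change 4.2.2, 6.3 and the Procedural Success entry in section 12 together:

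1. Use one assessment window throughout. Day 14/21 and 14 days must be reconciled; which is intended is for the sponsor to say.
2. State the scoring rule, for example: *All enrolled subjects (4.11) form the denominator. A subject not successfully stimulated by the end of the window, for any reason (wound not healed, explant, death, withdrawal), is not a technical success. Section 6.6 does not apply to this endpoint.*
3. Tabulate the reason for each non-success, so that a delay in healing can be told from a device failure.
4. Add a sensitivity analysis that excludes untested subjects.
5. Reconcile the wordings in 4.1, 6.3 and section 12 on whether stimulation must be effective or lower blood pressure. Report subjects who can be stimulated but have adverse effects at every setting as a separate line, without adding a discharge-based criterion.

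This concerns scoring only and alters no titration or discharge rule. It costs a few sentences and needs no new data, since 4.14 already provides for full follow-up of every enrolled subject. The downside is that the reported feasibility rate may be lower, and that a subject whose wound simply heals slowly counts against it; items 3 and 4 make that visible.

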6.4. Secondary Endpoints

- The change in blood pressure recorded during intraoperative stimulation at the time of implantation.
- Mean reduction in 24-hour ambulatory systolic and diastolic blood pressure (ambulatory blood pressure monitoring - ABPM) at one (1), three (3), six (6), twelve (12) and eighteen (18) and twenty-four (24) months post-treatment versus baseline.
- The composite MAE rate at 1, 3, 6, 12, 18 and 24 months post-procedure defined:
 - All-causes of death
 - Hospitalization for hypertensive crisis post-titration
 - Any device or procedure-related serious adverse event
- The mean reduction in office diastolic and systolic blood pressure, and diastolic and systolic blood pressure at 1, 3, 6, 12, 18, and 24 months.
- Changes in antihypertensive medicines/doses through 1, 3, 6, 12, 18 and 24 months post-implantation as analyzed by Daily Defined Dosages (WHO Definition) and total medications.
- Quality of Life as measured by the Medical Outcomes Study 36-Item Short-Form Health Survey (SF-36).

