Statistical Model	
• This is a single arm study in which each subject acts as his or her own control. Demographic variables will be tabulated in summary form. Adverse events will be tabulated and summarized. Outcome variables will be compared qualitatively to historical performance of other device-based therapies for hypertension.

2. Introduction and Background

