dose amounts." (Judd and Calhoun, 2014) Patients who require 4 or more medications to control blood pressure should also be considered resistant to treatment (Calhoun et al., 2008). Patients with pseudo-resistant hypertension have elevated blood pressure due to white-coat hypertension, improper blood pressure measurement or medication nonadherence (Judd and Calhoun, 2014) or secondary reasons for hypertension (Williams et al., 2018). For a better differentiation, some studies use the term apparent resistant hypertension, when $BP > 140/90$ mm Hg while taking ≥ 3 antihypertensive medications. If "pseudo-resistance can be excluded the differentiation of true resistance can be made from apparent resistance" (Calhoun et al., 2008). Therefore, the prevalence of true resistant hypertension is probably $<10\%$ (Calhoun et al., 2008; Williams et al., 2018). Nonadherence is one of the main causes of uncontrolled blood pressure (Brinker et al., 2014): Abegaz et al. found nonadherence in 45% of hypertensive patients, and in patients with poorly controlled BP, nonadherence was nearly 84% (Abegaz et al., 2017). Other studies reported a 47% prevalence of noncompliance (Strauch et al., 2013) and inadequate adherence or failing to take 75% of prescribed medications (Egan, 2015). Failure to comply with medical therapy for hypertension and the development of resistant hypertension clearly contribute to the continued high rates of cardiovascular disease attributable to hypertension (Daugherty et al., 2012; Pimenta and Calhoun, 2012).

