4.20. Baseline Assessment: Visit 2 (four weeks after visit 1)

- Office cuff blood pressure;

 neuroloop	Confidential	Protocol – The baroloop Study
--	---------------------	-------------------------------------

- Current medication history including all hypertensive medication including changes of medication regimen;
- Review and assessment of adverse events;
- 24 hour ambulatory blood pressure measurement (24hr ABPM) after observed therapy for hypertension.
- Medication compliance testing
- Quality of Life SF-36 questionnaire.

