4.25. Follow-up titration every 7 days (\pm 2-3 days)

- Clinical assessment of the subject;
- Physical examination;
- Changes of medication regimen;

 neuroloop	Confidential	Protocol – The baroloop Study
--	---------------------	-------------------------------------

- Review and assessment of adverse events;
- Office cuff blood pressure; and
- Titration of vagal nerve stimulation should be repeated weekly to achieve up to a 20% reduction in systolic blood pressure or office BP < the age-adjusted 2018 ESC/ESH treatment target office blood pressure (OBP), whichever blood pressure achieved during stimulation is lower. The titration protocol described above should be followed each time the patient returns for adjustment of baroloop stimulation. The data from the IPG will also be downloaded at each visit for subsequent analysis.

4.26. 30-Day Follow-up Visit (+7 / -7 days)

- Clinical assessment of the subject;
- Physical examination;
- Changes of medication regimen;
- Review and assessment of adverse events;
- Office cuff blood pressure;
- Medication compliance testing;
- 24hr ABPM after observed therapy for hypertension;
- Quality of Life SF-36 questionnaire; and
- Further testing and titration of stimulation to achieve an OBP less than the age-adjusted target of hypertension treatment, as described in the titration directions.

4.27. 90-Day Follow-up Visit (+14 / -14 days)

- Clinical assessment of the subject;
- Physical examination;
- Changes of medication regimen;
- Review and assessment of adverse events;
- Office cuff blood pressure;
- Medication compliance testing;
- 24hr ABPM after observed therapy for hypertension;
- Quality of Life SF-36 questionnaire; and
- Further testing and titration of stimulation to achieve an OBP less than the age-adjusted target of hypertension treatment, as described in the titration directions

4.28. 180-Day Follow-up Visit (+14 / -14 days)

- Clinical assessment of the subject;
- Physical examination;
- Changes of medication regimen;

 neuroloop	Confidential	Protocol – The baroloop Study
--	---------------------	-------------------------------------

- Review and assessment of adverse events;
- Office cuff blood pressure;
- Medication compliance testing;
- 24hr ABPM after observed therapy for hypertension;
- Quality of Life SF-36 questionnaire; and
- Further testing and titration of stimulation to achieve an OBP less than the age-adjusted target of hypertension treatment, as described in the titration directions

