6.1. Overview

The primary objective of this study is to characterize the safety and feasibility of the baroloop System in subjects with uncontrolled or resistant hypertension. All subjects will be followed on an intent-to-treat basis (ITT). The device performance will also be assessed based on a per-protocol analysis of the primary safety and feasibility endpoints and secondary efficacy endpoints. An intent-to-treat analysis, along with other secondary analyses, will also be completed and reported.

This is not a hypothesis driven study, and no formal power analysis or hypothesis-driven statistical analysis has or will be performed. Standard summary statistics will be calculated for all study variables. For continuous variables, statistics will include means, standard deviations, medians and ranges. Categorical variables will be summarized using frequency distributions.

The primary endpoints will be analyzed on an intent-to-treat (ITT) basis, for which data from all subjects enrolled will be included. In order to evaluate a true treatment effect, the primary analysis will include those subjects achieving technical success, the definition of which includes successful completion of the study procedure.

If there are no more than 4 failures to implant, combined with a safety level that is determined by the independent DSMB to be acceptable, together with any reduction in blood pressure as a result of the baroloop therapy, this will be considered a successful outcome to this First-in-Human study.

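### Office blood pressure, unlike ABPM, is not tied to observed dosing, and the compliance results feed no blood pressure analysis, so a rise in drug intake can be credited to the device

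*Combined protocol and SAP*

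**What the plan says.** - **Design.** Synopsis: "This is a single arm study in which each subject acts as his or her own control". Section 4.4: "Up to 10 subjects may be enrolled at up to 3 clinical study centers". Section 6.1: "This is not a hypothesis driven study, and no formal power analysis or hypothesis-driven statistical analysis has or will be performed".
- **ABPM.** Section 4.20 (Visit 2) lists "24 hour ambulatory blood pressure measurement (24hr ABPM) after observed therapy for hypertension". Sections 4.26 to 4.30 repeat that condition at 30, 90, 180 and 365 days and at 18 and 24 months. The observed-dosing condition in inclusion criterion 3 also applies to ABPM only.
- **Office pressure.** The same visit lists carry "Office cuff blood pressure" as a separate item, with no dosing condition. The section 6.4 endpoint is "The mean reduction in office diastolic and systolic blood pressure"; it names no baseline visit.
- **Compliance.** "Medication compliance testing" is scheduled at Visit 2 and at all six endpoint visits (sections 4.20 and 4.26 to 4.30; Table 3). Section 6 does not mention it. The only medication endpoint is change in medicines and doses, by Daily Defined Dosages and number of medicines.
- **Success.** Section 6.1 counts any fall in blood pressure attributed to the therapy towards a successful outcome, without saying which blood pressure measure is meant.

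**The concern.** Section 2.3 treats nonadherence as a leading reason for uncontrolled pressure and reports that "in patients with poorly controlled BP, nonadherence was nearly 84" percent. The plan guards against this for ABPM and collects compliance data, but carries neither safeguard over to the office pressure endpoint.

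With no control arm, nothing absorbs a change in drug intake between baseline and follow-up. The medication endpoint tracks the regimen, and section 4.34 asks for that regimen to be held, with no reduction before 6 months. A subject who takes more of an unchanged prescription would show a fall in office pressure and no change in Daily Defined Dosages. At stake are the office pressure endpoint, its qualitative comparison with other devices (Synopsis, Statistical Model), and the success criterion if it is read on office pressure.

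**Working it through.** The plan states no sample size calculation, error rate or expected effect, so there is no figure to reproduce. The check compares the visit lists with section 6 and then illustrates the size.

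**1. Visit lists against the analysis section**

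| Item | Baseline | Six endpoint visits | Use in section 6 |
|---|---|---|---|
| 24-hour ABPM | Visit 2, after observed therapy | After observed therapy | Change from baseline |
| Office cuff pressure | Visit 1, Visit 2, implantation day; no dosing condition | No dosing condition | Mean reduction; baseline visit not named |
| Compliance test | Visit 2 only | All six | Not named |
| Medicines and doses | Recorded | Recorded | Daily Defined Dosages, number of medicines |

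Per-protocol analysis is mentioned in section 6.1 but not defined, so compliance does not enter there either.

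**2. Change in contact**

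There are two baseline visits, four weeks apart. From Day 14 visits are twice weekly, then weekly. If weekly charging continues, the number of visits from Day 14 to Day 180 is:

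- switching to weekly at Day 30 (Table 3 footnote): 2 × (30 − 14)/7 + (180 − 30)/7 = 4.6 + 21.4 = 26.0
- switching after four weeks of titration, Day 42 (section 4.24): 2 × (42 − 14)/7 + (180 − 42)/7 = 8.0 + 19.7 = 27.7

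Subjects are also advised to keep taking their medicines (section 4.34).

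**3. Size with no device effect (assumed inputs)**

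Spurious mean fall = share of subjects moving to fuller intake × systolic fall in each.

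- 1 of 10 subjects, 10 mmHg each: 0.1 × 10 = 1 mmHg
- 4 of 10 subjects, 20 mmHg each: 0.4 × 20 = 8 mmHg

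A second route starts from the 47% noncompliance cited in section 2.3 (applying it to enrolled subjects is an assumption) and a fall of 5 to 20 mmHg per subject who resumes medicines (assumed):

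| Noncompliance at follow-up | Drop in share | Spurious fall, mmHg |
|---|---|---|
| 35% | 0.12 | 0.6 to 2.4 |
| 20% | 0.27 | 1.35 to 5.4 |
| 10% | 0.37 | 1.85 to 7.4 |

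As a yardstick, section 2.5.1 cites a reduction of about 3.6 mmHg for baroreflex activation therapy. The drop in noncompliance that alone would produce 3.6 mmHg is 3.6/10 = 36, 3.6/15 = 24 or 3.6/20 = 18 percentage points at 10, 15 or 20 mmHg per subject.

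**4. Success criterion, if read as a mean fall in office systolic pressure**

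Chance of any mean fall with no device effect = Φ(bias × √n / SD), with n = 10 and SD of change 10 to 20 mmHg (assumed):

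- bias 0: 50%
- bias 2.7 mmHg: 67% (SD 20) to 80% (SD 10)
- bias 3.6 mmHg: 3.6 × 3.162/20 = 0.57, giving 72%; 3.6 × 3.162/10 = 1.14, giving 87%

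**The case against.** The case on the other side has real force:

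- **No rise is shown.** Nothing in the documents establishes that adherence will improve, or by how much. This stands: the bias is possible, not demonstrated.
- **Order is open, not wrong.** Dosing is observed at the same visits as the endpoint office readings, and a site may well read office pressure afterwards. This stands: the gap is that the plan does not require it.
- **Compliance may be tabulated.** Section 6.1 promises summary statistics for all study variables, which can cover a compliance table by visit. This stands; what is missing is any link to the pressure changes.
- **ABPM is guarded and the primary endpoints do not use pressure.** Both stand. An artefact confined to office pressure would tend to show as disagreement with ABPM. However, no such comparison is planned, and with 10 subjects and an assumed SD of 10 to 20 mmHg for the difference, the 95% interval half-width is 2.262 × SD/√10 = 7.2 to 14.3 mmHg, too wide to reveal a few mmHg.
- **The cited rates come from a broader population.** Entry requires raised ABPM after observed dosing and a stable regimen (section 4.6.1). Section 4.5 invokes the ESC/ESH definition of resistance, which section 2.3 describes as requiring confirmed adherence. These limit baseline nonadherence without excluding it.

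A reader might infer that compliance testing itself intensifies to twice a week and drives adherence. Table 3 does not support that: there are six tests after implantation and none at the weekly visits.

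**Conclusion.** The point holds in a limited form. Office pressure need not be read after observed dosing at baseline or follow-up, and no pressure analysis uses the compliance results. In a one-arm before-and-after study with sharply increased contact, a rise in actual drug intake can be credited to the device in the office endpoint. The same applies to the success criterion if it is judged on office pressure.

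The size is unknown. About 1 to 8 mmHg is an illustration: the number of subjects changing and the gain in each are assumptions, and the documents give no source for the gain. It matters because the range spans the 3.6 mmHg cited for an existing device therapy.

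Two stronger readings are tempting but unsupported. One is that better pill-taking will in fact be counted as device effect; the documents show only that the plan could not tell the two apart. The other is that ABPM is equally exposed. It is measured after observed intake at both ends, so it is largely protected, though dosing observed for one measurement does not undo earlier partial intake. The primary safety and feasibility endpoints are not touched. This is a worthwhile, inexpensive improvement rather than a threat to the study's main conclusions.

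**What to change.** 1. **Sections 4.20 and 4.26 to 4.30.** Take the endpoint office reading at one stated point relative to the dose already observed for ABPM, identically at Visit 2 and every follow-up. Name Visit 2 as the office pressure baseline; Visit 1 has neither observed dosing nor a compliance test.
2. **Section 6.4.** List each subject's compliance result at Visit 2 and at the endpoint visit beside each office and ambulatory pressure change. State how compliance is classed, since these documents give no scale. As a descriptive sensitivity summary only, repeat the pressure changes in subjects with the same compliance class at both visits. A rule that dropped only subjects whose compliance rose would be one-sided: those whose compliance fell would stay in and pull the result against the device. Even the same-class summary selects on a variable measured after implantation, so it should not replace the main summary.
3. **Section 6.1.** Name ABPM after observed therapy as the blood pressure measure for the success criterion.

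The cost is possibly a short wait within existing visits and one extra summary based on fewer than 10 subjects. No new visits, tests or subjects are needed. Item 1 has to be settled before readings are taken, because office readings without a recorded dose time cannot be repaired later. Item 1 shares the limit noted for ABPM, that observed dosing does not undo earlier partial intake, which is why item 2 is needed alongside it.
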